#### Marking height of circumference measurement

The abdominal circumference measurement will be marked at **1cm Above Iliac Height** (middle height of the treated area circumference). Patient should stand up straight when arms are placed at the rear of neck and head is positioned towards the horizon (Figure 7). Elbows will be positioned in front of the body (Figure 7).

The height for the circumference measurement will be marked at the anterior abdomen, at the back and at each lateral side of the body. Additional measurements will be taken at: **Waist Height** (upper height of the treated area circumference) and at **1.5inch (3.81cm) Below Navel Height** (lower height of the treated area circumference) See Figure 6 below.

SYNERON CANDELA Syneron Medical Ltd. Confidential	Clinical Study to Evaluate the Safety and Efficacy of the SlimShape Device for Abdominal Fat and Circumference Reduction			
	Protocol #	DHF22621	Rev. Date	October 8, 2017

*Figure 6: Circumference measurements points*

*Figure 7: Body positioning during marking height for circumference measurement*

The **1cm Above Iliac Height, Waist Height and 1.5inch (3.81cm) Below Navel Height** will be measured using the height measuring device (supplied by Syneron Medical). The marking pencil will be placed horizontally at the stage of the measurement device during the marking procedure. (Figure 7)

**Height of all measurements point will be recorded in the CRF** (will used as reference for the next visits measurements). As well, the **circumference results of each height** will be recorded at each visit.

### Measuring Circumference

Abdominal circumference is measured to quantify the treatment effect. This procedure will be performed and recorded every visit at the clinic, immediately following the measurement of height marking.

In order to achieve reproducible measurement results, the following requirements should be fulfilled:

1. Patient should be wearing underwear and barefoot during circumference measurement.
2. Patient should stand up straight when arms are placed at the rear of neck and head is positioned towards the horizon. Elbows will be positioned in front of the body (see Figure 8A).
3. The measurement tape (supplied by Syneron Medical) should be in parallel to the floor during the measurement (see Figure 8B).
4. The circumference measurement tape should be placed under the marked reference points, in order to maintain repetitive height of the measurement.

SYNERON CANDELA Syneron Medical Ltd. Confidential	Clinical Study to Evaluate the Safety and Efficacy of the SlimShape Device for Abdominal Fat and Circumference Reduction			
	Protocol #	DHF22621	Rev. Date	October 8, 2017

5. Middle measurement should be taken at the level of the 1cm Above Iliac Height. Additional two circumference measurements at Waist Height and 1.5inch (3.81cm) Below Navel Height will be taken. This height levels should be recorded for follow up assessments.
6. Consecutive measurements should be performed at the same height recorded at baseline. In order to assure that the measuring tape is parallel to the floor, several reference points should be marked around the treatment area and the measuring tape should be placed such that it is aligned with them.

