## 5. Subject improvement and satisfaction:

Improvement and satisfaction assessment will be performed independently by the subject using a pre-defined scale questionnaire. The subjects will answer this questionnaire at each follow-up visit (4wk FU, 8wk FU and 12wk FU)

 Syneron Medical Ltd. Confidential	Clinical Study to Evaluate the Safety and Efficacy of the SlimShape Device for Abdominal Fat and Circumference Reduction			
	Protocol #	DHF22621	Rev. Date	October 8, 2017

Efficacy Endpoints	Primary and secondary objectives will be measured using the next efficacy endpoints: 
 
1. Fat thickness measurements using Ultrasound device
 
2. Fat thickness measurements using Caliper
 
3. Circumference measurements of the abdominal area using Measuring Tape
 
4. Investigator satisfaction using a pre-defined scale
 
5. Subject improvement and satisfaction using a pre-defined scale
 
6. Photography
 

Safety Endpoints	
 
1. The number, severity and type of any adverse event recorded throughout the study and post treatment (immediate and delayed response)
 

Statistical Methods	Descriptive statistics will be used to present changes in the assessments along the study course. Circumference measurements and subject assessments' and satisfaction data will be analyzed using two-tailed Wilcoxon Signed Rank test and/or paired t-test (alpha=0.05) to analyze the data difference from baseline and longitudinal change.

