**STUDY DESIGN OVERVIEW**

This study is a prospective, baseline controlled, multi-center, one arm clinical study showing the performance and safety of the SlimShape treatment for abdominal non-invasive fat and circumference reduction.

Up to 120 Healthy subjects in up to 10 investigational sites will be enrolled in this study. All subjects will undergo an assessment of their general health. During the treatment period, subject's fat thickness and circumference will be measured and up to three successive bi-weekly (two weeks interval) treatments will be performed.

The study subjects will undergo treatments with SlimShape device utilizing the SlimShape Applicator Belt.

During the follow-up period visit will be conducted as follow: 4 weeks (4wk FU), 8 weeks (8wk FU) and 12 weeks (12wk FU) post last treatment. Subject's fat thickness will be measured using 2 different methods (Calibrated Caliper and Ultrasound Imaging (USI)) and fat reduction will be assessed at each post baseline visit. Circumference will be measured in 3 measurements heights and circumference reduction will be assessed at each post baseline visit. Additionally, investigator and subject questionnaires will be completed. Finally, photography will be performed under visible light conditions of the front, right, left and back view. Most of the assessments will occur at each of the visits to the clinic.

 Syneron Medical Ltd. Confidential	Clinical Study to Evaluate the Safety and Efficacy of the SlimShape Device for Abdominal Fat and Circumference Reduction			
	Protocol #	DHF22621	Rev. Date	October 8, 2017

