### **Secondary Objectives**

1. Statistically significant abdominal fat reduction post SlimShape treatments as measured by USI device at Pre Tx.3, 4 weeks, and 8 weeks follow-up (4wk FU and 8wk FU) versus baseline.
2. Statistically significant abdominal fat reduction post SlimShape treatments as measured by Calibrated Caliper device at Pre Tx.3, 4 weeks, and 8 weeks follow-up (4wk FU and 8wk FU) versus baseline.
3. Statistically significant abdominal circumference reduction post SlimShape treatment/s at Pre Tx.2, Pre Tx.3, 4 weeks, 8 weeks and 12 weeks follow-up (4wk FU, 8wk FU and 12wk FU) versus baseline.
4. Investigator satisfaction:  
Satisfaction assessment will be performed by the study investigator using a pre-defined scale questionnaire. The investigator will answer this questionnaire at each follow-up visit (4wk FU, 8wk FU and 12wk FU).
5. Subject improvement and satisfaction:  
Improvement and satisfaction assessment will be performed independently by the subject using a pre-defined scale questionnaire. The subjects will answer this questionnaire at each follow-up visit (4wk FU, 8wk FU and 12wk FU).

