## **STUDY POPULATION**

### **Number of Subjects**

This study will be comprised of up to 120 subjects in up to ten (10) investigational sites. Subjects who meet all the inclusion and none of the exclusion criteria will be enroll.

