**Figure 5: Ultrasound Measurements Points**

[figure not shown]
- Mark the treated area and the measurements points on the transparency, to ensure measurement of the same point in each subsequent visit.

- d) Ultrasound measurements should be obtained from the edges of the measurement points, laterally (see **Figure 5 above, yellow dashed lines**).
- e) Place the applicator on the skin surface at angle of 90° (located the applicator under the measurement point line for consistency).
- f) Measurement should include all the area between the dermis and end of the fat tissue fascia. At least 2 measurements should be done in each measurement point.

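### Circumference is taped once per height per visit; a second reading, above all at baseline, would be a cheap precision gain for secondary objective 3

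*Combined protocol and SAP*

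**What the plan says.** Under Study Design Overview, "Circumference will be measured in 3 measurements heights". Measuring Circumference, item 5, sets out the readings: "Middle measurement should be taken at the level of the 1cm Above Iliac Height", and then "Additional two circumference measurements at Waist Height and 1.5inch (3.81cm) Below Navel Height will be taken". That is three readings over three heights, one each. No section asks for a repeat, a mean or a tolerance between repeats. Item 6 (later measurements at the recorded height) and item 8 (re-measurement by the same operator at a similar hour) concern later visits and are not replicate rules.

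For ultrasound, step f of the measurement procedure says "At least 2 measurements should be done in each measurement point".

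Secondary objective 3 is "Statistically significant abdominal circumference reduction post SlimShape treatment/s at Pre Tx.2, Pre Tx.3, 4 weeks, 8 weeks and 12 weeks follow-up", each against baseline. Table 2 and Appendix I schedule circumference before each of the three treatments and at the three follow-up visits, so there is one baseline and five later visits. The Statistical Methods row of the Study Synopsis names circumference for a "two-tailed Wilcoxon Signed Rank test and/or paired t-test (alpha=0.05"). On sample size, "This study will be comprised of up to 120 subjects"; no effect size, SD, reading error or power is given.

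**The concern.** Each circumference result is a later reading minus a baseline reading, so the variance of reading error enters every change score twice. The baseline part is common to all of a subject's change scores at that height. The Pre-Treatment Procedures expect screening, baseline and Tx.1 at one visit, and an untreated baseline cannot be obtained after that. If the tape is misread at baseline and nobody repeats the reading, the error stays in that subject's data at that height for the whole study.

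The protocol already uses replicates for one instrument and gives no reason for leaving them out with the tape. By the time of the first reading the subject has fasted, undressed, been positioned and been marked, so most of the effort has been spent. What is at stake is the precision of a secondary endpoint that also appears in the study title and overall objective.

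**Working it through.** The plan has no figure to reproduce, because it gives no sample-size calculation.

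**Inputs from the documents.** One reading per height, three heights, one baseline and five later visits; n up to 120; two-sided alpha 0.05; paired analysis.

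**Assumed input.** Let Ve be the within-visit reading-error variance and Vd the variance of everything a repeat cannot reduce (true change and visit-to-visit variation). With k readings averaged at each visit, at one height:

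Var(change) = Vd + 2Ve/k.

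Let r = 2Ve/(Vd + 2Ve), the share of change-score variance due to reading error when k = 1. The documents do not give r; it is ranged from 0.1 to 0.5.

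**Two readings at every visit.** With independent repeat errors, the variance ratio is 1 − r/2. The detectable mean change at 80% power with single readings is (1.960 + 0.842)/√120 = 0.2557 SD of change. With duplicates it is that value times the SE ratio.

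| r | Variance ratio | SE ratio | Equivalent n with single readings (120/ratio) | Detectable change (single-reading SDs) | 80% power becomes |
|---|---|---|---|---|---|
| 0.1 | 0.95 | 0.975 | 126 | 0.2493 | 82% |
| 0.2 | 0.90 | 0.949 | 133 | 0.2426 | 84% |
| 0.3 | 0.85 | 0.922 | 141 | 0.2358 | 86% |
| 0.5 | 0.75 | 0.866 | 160 | 0.2215 | 90% |

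**Two readings at baseline only.** Var(change) = Vd + Ve/2 + Ve, so the ratio is 1 − r/4: 0.975 at r = 0.1 and 0.875 at r = 0.5. A comparison with 80% power rises to 81% to 85%, and this applies to all five comparisons.

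**Correlated repeat errors.** If two readings at one visit have error correlation ρ, the ratio is 1 − r(1 − ρ)/2. At ρ = 0.5 it is 0.975 to 0.875, half the variance saving in the table.

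**Three heights averaged.** With a common true change and independent errors, the variance goes from (1 − r) + r/3 to (1 − r) + r/6. The ratio is 0.9167/0.9333 = 0.98 at r = 0.1 and 0.5833/0.6667 = 0.875 at r = 0.5.

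**In centimetres.** Assume Vd = 2² and a reading-error SD, e, of 0.5 to 1.0 cm.
- e = 0.5: variance 4.5 falls to 4.25 and SD 2.12 to 2.06 (3% lower). Detectable change goes from 0.2557 × 2.121 = 0.54 cm to 0.2557 × 2.062 = 0.53 cm.
- e = 1.0: variance 6 falls to 5 and SD 2.45 to 2.24 (9% lower). Detectable change goes from 0.63 cm to 0.57 cm.

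**Third readings.** Two readings differ with SD e√2. The chance of a gap above 1 cm, with normal errors, is about 16% at e = 0.5 and 48% at e = 1.0. Expected extra readings per visit are 3 × 1.16 = 3.5 and 3 × 1.48 = 4.4.

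**The case against.** The case for leaving the procedure alone has real force. Nothing in the plan is contradicted and no analysis is made invalid. The primary measure, ultrasound at 12 weeks, already has replicates, and putting them there rather than on a secondary measure is a defensible choice. The contrast with ultrasound is therefore not an error in itself.

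The tape procedure is also far from uncontrolled. Posture, marked heights, a level tape, a constant-tension device and three hours of fasting are all specified, and the same operator at a similar hour is recommended. An immediate repeat on the same marks by the same person does not reduce most of the error those rules address, so the table above is an upper bound for any given reading error. On the centimetre assumptions, the detectable change improves by only about 0.15 to 0.55 mm.

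A reader might infer that one misread corrupts the five circumference comparisons for the trial. The documents do not support that. It affects one height of three in one subject: a 5 cm misread among 120 subjects moves a mean change by 5/120 = 0.04 cm. The signed rank test would limit its leverage further, although the and/or wording leaves the t-test possible. A shared baseline is part of any baseline-controlled design, and duplicates do not remove it.

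What stands is that none of the existing rules averages out reading error within a visit or shows a misread while it can still be corrected. The protocol does not forbid repeats, but without a written rule the sites, up to ten of them, may differ.

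**Conclusion.** The point holds as a cheap improvement to a secondary endpoint. One reading per height is the plain count in item 5, and the baseline reading is used in up to five comparisons (fewer for a subject given fewer than three treatments). If independent reading error is 10% to 50% of the change-score variance at one height, duplicates cut the standard error by about 2.5% to 13%. The gain is smaller with correlated repeats or if the heights are averaged, and the documents do not say how the three heights enter the analysis. The percentages do not depend on n; the detectable changes assume n = 120.

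It would be tempting to read this as a bias in the circumference result, or as a loss of known size. Neither follows. Independent random reading error widens the interval without shifting the mean change, and no document gives the error needed to fix the size. Duplicates would not remove operator bias or day-to-day variation.

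**What to change.** In Measuring Circumference, specify two consecutive readings at each height, with the tape removed and re-applied between them. Take a third if the two differ by more than a pre-set tolerance, for example 1 cm. Record every reading in the CRF and analyse the mean, or the median where there are three. If this is too much at every visit, do it at baseline at least, where it serves all five comparisons.

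The cost at every visit is about 3.5 to 4.4 extra readings including third readings (error SD 0.5 to 1.0 cm assumed, 1 cm tolerance), plus fields on the paper CRF. Before third readings that is 3 × 6 = 18 extra per subject, or 2,160 over 120 subjects. At baseline only it is 3 per subject, or 360 in all, again before third readings. No extra visits or staff are needed. The documents give no timings, so the time cost is a judgement.

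The 1 cm tolerance should not be carried over to the caliper: it is an example for girth and has no basis for fat thickness.

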**Figure 8: Patient positioning during circumference measurements (A) and measuring device position around the abdomen (B)**

7. The measurement device should be activated at a constant tension to achieve an exact measure of the circumference (use measurement device supplied by Syneron only).
8. In order to minimize measurement inaccuracies originating from human error, it is recommended that, whenever possible, the same operator re-measures the patient at approximately at the same hour of day ( $\pm 3$  hours).
9. Patients should be under fasting for at least 3 hours prior to circumference measurement.

### **Treatment Procedure**

Subjects will receive treatments with SlimShape device utilizing the SlimShape Applicator Belt on the anterior abdomen.

Prior to each treatment measurements of weight, fat thickness (by Caliper & Ultrasound), and abdominal circumference will be done according to the references from the enrollment visit

 Syneron Medical Ltd. Confidential	Clinical Study to Evaluate the Safety and Efficacy of the SlimShape Device for Abdominal Fat and Circumference Reduction			
	Protocol #	DHF22621	Rev. Date	October 8, 2017

(Baseline/ prior to Tx.1). Only patients who are eligible for treatment will be allowed to undergo the SlimShape procedure.

Enrolled subjects will undergo up to 3 successive (according to investigator decision) bi-weekly (2 weeks interval) treatments (Tx.1, Tx.2 and Tx.3). Additional three (3) visits in the clinic will be occurred to follow-up the abdominal fat and circumference reduction at visits 4, 5 and 6 (4 weeks, 8 weeks and 12 weeks following last treatment).

## **SlimShape Treatment Procedure**

### General Treatment Instructions

1. Place the patient so that he/she is lying on his/her back, with the legs extended. In this position, the abdomen is fully accessible and treatment can be easily performed.
2. Remove any jewelry in the area of the application site.
3. Ensure that the subject skin in the entire treatment is clean. The skin should be cleaned with water and soap and hairs that exist in the treatment areas will be shaved.
4. Ensure that the applicator belt is clean or wipe with 70% alcohol and allowed to dry.
5. The choice of treatment settings should take into consideration not only the severity of the treated condition (fat layer), but also the subject's skin type, tendency to bruise, the specific anatomical location (abdomen), and comfort.
6. Immediately prior the treatment, apply a generous amount of the commercial VelaEase treatment lotion, RF coupling lotion. You may need to re-apply the lotion if required.
7. Position the SlimShape Applicator Belt at the correct/ chosen treatment area (on the abdomen).
8. There should be a complete seal between the applicator and the skin during the treatment session. If you hear air being sucked into the chamber, this indicates that the contact between the skin and the belt chambers is not ideal for vacuum creation. This usually means that the applicator is not positioned properly at that moment, which tends to happen in curved or bony areas, so special attention is required when treating such areas. Changing the orientation of the applicator slightly may solve this problem.
9. The applicator belt chambers should have equal compression/contact with the skin to ensure safe and effective RF delivery.
10. Secure the magnetic pads on the sides of both belts, on both sides of the patient and tight the SlimShape belt.
11. Select the desired treatment protocol.

 Syneron Medical Ltd. Confidential	Clinical Study to Evaluate the Safety and Efficacy of the SlimShape Device for Abdominal Fat and Circumference Reduction			
	Protocol #	DHF22621	Rev. Date	October 8, 2017

12. Full operating procedure, software screens and parameters are described in the device user manuals and instruction will be provided prior to the start of the study.
13. Expected post treatment side effects are limited to Erythema (blanchable/non-blanchable), Edema, Heat sensation, Hematoma and Pain sensation.

 Syneron Medical Ltd. Confidential	Clinical Study to Evaluate the Safety and Efficacy of the SlimShape Device for Abdominal Fat and Circumference Reduction			
	Protocol #	DHF22621	Rev. Date	October 8, 2017

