### **Primary Safety Endpoint**

The number, severity and type of any adverse event recorded throughout the study and post treatment (discomfort (pain), immediate and delayed response).

1. Occurrence of expected post treatment immediate response including erythema and edema and during all study period based on predefined scale (Table 4).
2. Number, severity and type of any adverse event recorded throughout the course of the study.

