## **ADVERSE EVENTS (AE)**

An adverse event (AE) is any adverse change in health or side effect that occurs in a study participant during their participation in the study.

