### **Anticipated Adverse Effects**

Following treatment with the *SlimShape* the following local adverse effects could occur (anticipated):

- Purpura
- Blister
- Bruising
- Bullae
- Erosion
- Pain/ soreness
- First degree burn
- Second degree burn

An adverse event (AE) is any undesired clinical occurrence in a study subject as indicated by signs, symptoms, illnesses, events that develop or worsen in severity in association with the study when deemed by the Investigator to be related to use of the device or study procedures. The Investigator will document all adverse signs and symptoms regardless of severity or frequency that are either volunteered by subjects or observed during the course of the study that are related to the device. The Investigator will also record adverse experiences of subjects resulting from concurrent illnesses, reactions to concurrent medications, or progression of disease states that the Investigator deems related to the device. Included in the description will be the nature of the sign or symptom, the date of onset, whether the event was serious, the severity, the relationship to study procedures or investigational device, the action taken, the date of resolution, and the outcome. The Principal Investigator will determine the relationship of the adverse device effect to the investigational device.

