**All unanticipated adverse effects will be graded as follows:**

**Mild:** Sign or symptom, usually transient, non-life-threatening requiring no special treatment and generally not interfering with usual activities.

**Moderate:** Sign or symptom, non-life-threatening which may be ameliorated by simple therapeutic measures, and may interfere with usual activity.

**Major:** Sign or symptom that is intense or debilitating but non-life-threatening and that interferes with usual activities. Recovery is usually aided by therapeutic measures and the discontinuation of the study device may be required.

**Severe:** Any untoward medical occurrence that at any time results in death or life-threatening illness, resulting in persistent or significant disability/incapacity.

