**Reporting Adverse Events (AE) and Serious Adverse Events (SAE)**

**Anticipated Adverse Events:** Anticipated adverse events in this study include Purpura, blistering, bruising, bullae, erosion, soreness and burn. If an unanticipated adverse event occurs at any time during or after the use of the SlimShape device, the Investigator must report it to Syneron.

The Investigator must report all unanticipated adverse device effects that are serious in nature to the clinical study monitor immediately or within twenty-four hours by telephone (see below). If such an unanticipated adverse device effect is reported after normal working hours, the Investigator will leave a voice message at the monitor's telephone number with accompanying report of the unanticipated adverse device effect faxed or sent to the fax number/e-mail address below:

 Syneron Medical Ltd. Confidential	Clinical Study to Evaluate the Safety and Efficacy of the SlimShape Device for Abdominal Fat and Circumference Reduction			
	Protocol #	DHF22621	Rev. Date	October 8, 2017

[name], Global VP of Clinical Affairs  
Telephone/Fax No.: From the U.S. [name]  
[name] (cell)  
E-mail: [contact]

A written report prepared by the Principal Investigator must follow within five working days to both the IRB and to Syneron and should include a full description of the event and sequence.

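### Expected side effects and anticipated adverse events are listed, defined and graded inconsistently, so one skin finding can enter either or both components of the primary safety endpoint

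*Combined protocol and SAP*

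**What the plan says.** The document is the combined protocol and SAP (the protocol below).

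- **Effects of treatment.** Item 13 of the General Treatment Instructions gives a closed list of five: "Expected post treatment side effects are limited to Erythema (blanchable/non-blanchable), Edema, Heat sensation, Hematoma and Pain sensation". The section Anticipated Adverse Effects lists eight: purpura, blister, bruising, bullae, erosion, pain/soreness, and first and second degree burn. The Risks section repeats those eight. The section on reporting adverse events has a shorter version: "Anticipated adverse events in this study include Purpura, blistering, bruising, bullae, erosion, soreness and burn".
- **Primary safety endpoint.** The first component is "Occurrence of expected post treatment immediate response including erythema and edema and during all study period based on predefined scale (Table 4"). The second is "Number, severity and type of any adverse event recorded throughout the course of the study".
- **Adverse event definition.** The Adverse Events section opens with a broad one: "any adverse change in health or side effect that occurs in a study participant during their participation in the study". The subsection Anticipated Adverse Effects then gives a narrower one, limited to undesired occurrences that the investigator judges related to the device or study procedures.
- **Severity.** Post Treatment Procedures sends visible and palpable immediate responses to Table 4, which has grades 0 to 3 labelled absent, mild, moderate and severe, without definitions. A second scale (mild, moderate, major, severe), with definitions, is introduced by "All unanticipated adverse effects will be graded as follows".

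**The concern.** The primary safety endpoint consists of the number, severity and type of adverse events. All three depend on which list, definition and scale a site follows, and the protocol does not settle any of them. With up to 10 sites, different sites can record the same finding differently, each with support in the text. The trial has one arm, so no comparator group shares the misclassification and offsets it. The Risks section also rests on earlier experience in which all reported events were mild. Comparing this study with that experience needs stable categories and a stable severity scale.

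**Working it through.** No sample size or error rate is involved, and the protocol gives no figure to reproduce. The check sets the lists side by side and then follows individual findings through the counting and grading rules.

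**Step 1. The lists.**

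| Effect | Item 13 (5 terms) | Anticipated Adverse Effects and Risks (8 terms) | Reporting section (7 terms) |
|---|---|---|---|
| Erythema | yes | no | no |
| Edema | yes | no | no |
| Heat sensation | yes | no | no |
| Hematoma | yes | not by that name | not by that name |
| Pain | yes | yes, as pain/soreness | soreness only |
| Bruising | not by that name | yes | yes |
| Purpura | not by that name | yes | yes |
| Blister | no | yes | yes |
| Bullae | no | yes | yes |
| Erosion | no | yes | yes |
| First degree burn | no | yes | yes, as burn |
| Second degree burn | no | yes | yes, as burn |

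By name, only pain is shared between the first two lists: 5 − 1 = 4 terms are on the expected list only, and 8 − 1 = 7 on the anticipated list only. If hematoma is taken to mean the same as bruising and purpura, 5 − 2 = 3 remain on the expected list only (erythema, edema, heat sensation). Then 8 − 3 = 5 remain on the anticipated list only (blister, bullae, erosion, both burn grades). Even on this more generous matching, the closing words of item 13 exclude 5 of the 8 effects that the adverse event section says could follow treatment.

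**Step 2. Counting.**

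- *Erythema.* It is a named immediate response, so it enters component 1 on Table 4. Item 13 calls it a side effect, and the general definition makes every side effect an adverse event, so it also qualifies for component 2. Under the narrower definition it qualifies if the investigator judges it undesired and related.
- *Bruise.* Recorded as hematoma, it is an expected side effect. Recorded as bruising or purpura, it is an anticipated adverse event.
- *Pain.* It is on both lists. The Treatment Visit paragraph under Data Analysis also has pain scores documenting adverse events, but Appendix II contains no separate pain scale.

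Timing does not separate the components. Table 2 schedules the immediate response assessment only directly after each treatment. The endpoint extends component 1 over the whole study, and Return Visits asks for post-treatment response and adverse events together at each follow-up. The same finding therefore has three permissible routes: component 1 only, component 2 only, or both.

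The two definitions also differ for events not judged related. An unrelated illness is an adverse event under the broad definition and not under the narrow one.

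**Step 3. Grading.**

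| Finding | Scale assigned | Meaning of Severe |
|---|---|---|
| Immediate response | Table 4 | not defined |
| Unanticipated effect | mild / moderate / major / severe | death, life-threatening illness or disability |
| Anticipated adverse event | none stated | none stated |

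An intense but non-life-threatening reaction is Major on the second scale and could be graded Severe on Table 4.

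**Step 4. Size.** If a fraction p of subjects has such a finding and no other adverse event, the proportion with at least one adverse event differs by p between recording it as an adverse event and not doing so. The documents give no value or range for p, so no numerical effect follows.

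**The case against.** The strongest defence is that the protocol intends two tiers. Post Treatment Procedures separates immediate clinical effects from adverse events, the endpoint has two components, and Table 2 gives them separate rows. Item 13 closes the treatment instructions and may mean only routine immediate effects. One sign can be a transient response in one subject and a lasting adverse event in another, so overlap of terms is not in itself a contradiction. This shows the likely intent. It does not supply the boundary: the general definition takes in side effects, component 1 runs throughout the study, and no rule says when a response becomes an event.

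Table 2 also mentions an adverse event form with severity ratings. That form is not in the documents and may define a scale, but the protocol text does not say so.

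The protocol states no safety hypothesis or threshold, and events are recorded by type, so erythema could be tabulated on its own. That limits the consequence. It does not help where sites differ on whether to record the finding as an adverse event at all.

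A reader might go further and infer that routine erythema, being absent from the anticipated lists, is an unanticipated event that must be reported to the sponsor and graded on the second scale. The documents do not support that. The section Unanticipated Adverse Device Effects requires a serious effect not previously identified in the plan. Erythema and edema are named as expected in the endpoint section and in item 13, and heat sensation in item 13. The reporting section says only that anticipated events include its seven terms, and its 24-hour telephone report covers serious unanticipated effects. What remains is that the same section uses the looser term unanticipated adverse event without defining it.

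**Conclusion.** The point holds as an internal inconsistency in the definition of the primary safety endpoint. The closed list in item 13 conflicts with the anticipated lists on 5 of 8 effects, if hematoma is equated with bruising and purpura. Erythema, bruise and pain can each be counted in component 1, component 2 or both. Two severity scales give Severe different meanings, and anticipated adverse events have no assigned scale. For anticipated bruising or pain, the grading defect on the adverse event side is therefore a missing scale, not two competing ones. For pain and bruising the trouble lies in counting and grading; sponsor reporting is not affected if hematoma and bruising are treated as the same. The conclusion rests on the protocol text alone and assumes that no form or manual outside it resolves these points. How far event rates would move is unknown.

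**What to change.** Reconcile these places: Primary Safety Endpoint, General Treatment Instructions item 13, Post Treatment Procedures, the opening of Adverse Events, Anticipated Adverse Effects, the grading of unanticipated effects, the reporting section, Risks, and Table 4.

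1. Use one term list throughout, with synonyms such as hematoma, bruising and purpura either merged or defined apart, and delete the words *are limited to* from item 13.
2. Keep one adverse event definition, and say whether events judged unrelated are included.
3. State a rule for when an immediate response is also recorded as an adverse event. Do not assign each effect permanently to one tier, since that could hide persistent or severe erythema.
4. Report the two endpoint components separately, and state how a finding that qualifies for both is handled so that it is not counted twice.
5. Grade every adverse event, anticipated or not, on one defined severity scale. If Table 4 is kept for immediate responses, define its grades and avoid using Severe with two meanings.

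The cost is protocol wording and a revision of the adverse event form. It needs no extra visits, measurements or subjects.
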